This study involves research, and the purpose of this study is to evaluate live birth rates among couples who are treated by Natural procreative technology, (NPT) for infertility and miscarriage.

Comparisons will be made to those declining NPT treatment, waiting for NPT treatment, receiving other treatment, or stopping treatment. We seek to document specific pregnancy rates for different factors such as age and type of infertility diagnosis. We will also assess characteristics of environmental exposures that may be associated with infertility. Couples will be followed for up to three years, regardless of when they begin NPT treatment, or whether they continue treatment. We are seeking the broadest possible participation from couples who are considering NPT treatment. Data from all couples will be useful for this study, regardless of their individual circumstances or actual treatment.

Page numbers from a sponsor's protocol/grant may be referenced in 2b and 2c.

Protocol Title: Natural Procreative Technology Evaluation and Surveillance of Treatment for Infertility and Miscarriage

b) List your research objectives (specific aims & hypotheses of the study).

This is an exploratory study rather than a hypothesis testing study. This study aims to determine what the live birth rates are over time for patients who are treated with natural procreative technology (NPT) for infertility or history of spontaneous abortion, and how the live birth rate may vary by patient characteristics, especially the age of the woman, prior pregnancy, and underlying diagnoses. Secondary analyses will explore outcomes of conceptions (live birth versus other outcomes) and the association of environmental exposures with infertility. This is an observational study: there will be no intervention. Patients will receive whatever care they choose to receive. Couples receiving NPT treatment will be compared to those declining NPT treatment, waiting for NPT treatment, receiving other treatment, or stopping treatment. Interventions received, conceptions, and outcomes of conceptions will be followed for up to 3 years for each couple entering the study.

Please save frequently

c) Describe the study design (e.g., single/double blind, parallel, crossover, control, experimental, observational, etc.). If the study is investigator-initiated, a timeline for individual subject recruitment, follow-up, and analysis for the study is required. Also, indicate if the subjects will be randomized.

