The Woman's Entrance Questionnaire will be completed by the subject at the time of their initial visit or as soon as possible per SOC. Following enrollment into the study, the subject will complete the following questionnaires:

- Women's Update Questionnaire on an annual basis (from the date of completion of the Women's entrance questionnaire) for up to 3 years (research related),
- Pregnancy Outcome Questionnaire for any pregnancy (research-related),
- Women's Exit Questionnaire whenever they exit the study (research-related).

Depending on the timing of subject enrollment, any follow-up questionnaire time point which may have already occurred at the time of subject enrollment will be considered skipped. Questionnaires may be done by mail, email or telephone. Each questionnaire will take approximately 30-45 minutes to complete.

For male partners:

The Men's Entrance Questionnaire will be completed per SOC (may be completed before or after enrollment into the study).

Following enrollment into the study, the subject will complete the following questionnaires:

- Men's Update Questionnaire on an annual basis (from the date the female partner completed the Women's entrance questionnaire) for up to 3 years (research-related),
- Men's Exit Questionnaire whenever they exit the study (research-related).

Depending on the timing of subject enrollment, any follow-up questionnaire time point which may have already occurred at the time of subject enrollment will be considered skipped. Questionnaires may be done by mail, email, or telephone. Each questionnaire will take approximately 30-45 minutes to complete.

- 2) The subject's own Creighton Model fertility charts. (The Creighton Model Fertility charts teaches couples to recognize, understand, and record the changes that occur during the fertility [menstrual] cycle. These changes [biomarkers] indicate whether the reproductive system is functioning normally or not. It also identifies ovulation and other key events. It is completely natural and cooperative with a woman's fertility [menstrual] cycle).
- 3) Information about NPT treatment and pregnancies from the medical records of their NPT physician(s) (prospective and/or retrospective, based on the timing of consent)..

This data collection will continue for up to three years after enrollment into the study (research related).

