- d) Describe how data analysis will be performed (statistical tests, methods of evaluating data) and indicate the smallest group/unit for which separate reporting will occur. For studies involving a questionnaire, if data and reliability information are available, please describe or provide references. For full board, unfunded studies describe sample size determination and power analysis. If none, please justify.

The database exists in Microsoft Access. Analyses will be done in Excel (for basis of descriptions), SAS and/or SPSS statistical computer programs. As stated above, data used in the analysis will be aggregate data, and will not contain any individual identifiers. Therefore, there will be no possibility of identifying individual respondents during the analysis or in the reporting of the final results.

Analysis of Main Outcome

The main outcome of this study is the proportion of subjects that had a live birth at various time points up to five years after beginning treatment with NPT, compared to couples who do not receive NPT treatment, or who cease to receive NPT treatment. This will be analyzed by standard lifetable techniques to deal with censored data (i.e., couples for whom pregnancy status cannot be ascertained beyond a certain time period). Cox proportional hazards regression will be used in an exploratory manner to investigate demographic and medical characteristics (particularly woman's age, prior pregnancy, and associated medical diagnoses) that may be associated with a greater likelihood of successful live birth. The same set of analyses will be repeated for the secondary outcome of conception (clinical pregnancy).

Analysis of Secondary Outcomes

Initially, all secondary outcomes will be analyzed as simple proportions, e.g., of couples who conceived, what proportion had a live birth, spontaneous abortion, or other pregnancy outcome.

Protocol Title: Natural Procreative Technology Evaluation and Surveillance of Treatment for Infertility and Miscarriage

conceived, what proportion had a live birth, spontaneous abortion, or other pregnancy outcome. Where indicated by the initial analysis, supplementary analyses using standard statistical techniques may be employed (e.g., a logistic regression with the outcome of live birth versus other pregnancy outcome).

Sample Size

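### The NPT comparison in the main outcome has no time origin for untreated couples, no rule for changes of status and no delayed entry for late consent

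*Combined protocol and SAP*

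**What the plan says.** Item 3d, Analysis of Main Outcome, takes the proportion with a live birth at successive times "after beginning treatment with NPT, compared to couples who do not receive NPT treatment, or who cease to receive NPT treatment". The method is "standard lifetable techniques to deal with censored data (i.e., couples for whom pregnancy status cannot be ascertained beyond a certain time period"), and no other kind of censoring is named. The Cox model in the same item is described for patient characteristics; NPT status is not listed as a covariate.

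The objectives (item 2b) widen the comparison: "Couples receiving NPT treatment will be compared to those declining NPT treatment, waiting for NPT treatment, receiving other treatment, or stopping treatment". The lay summary (2a) expects changes of status: "Couples will be followed for up to three years, regardless of when they begin NPT treatment, or whether they continue treatment". Item 2b also states "This is an exploratory study rather than a hypothesis testing study".

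On timing, item 3b says "The Woman's Entrance Questionnaire will be completed by the subject at the time of their initial visit" or soon after, and "This data collection will continue for up to three years after enrollment into the study". Medical-record data are "prospective and/or retrospective, based on the timing of consent". Item 13 allows consent at the first consultation or at any later visit. Inclusion criterion 1 (item 8h) admits couples trying to conceive and also couples who come for help in keeping a pregnancy.

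**The concern.** A couple that never takes NPT has no date of beginning NPT, so the stated clock does not exist for it. The enrolment and questionnaire dates in item 3b govern data collection and are not named as an analysis origin. A couple that waits, starts and later stops belongs to several comparison groups in turn, and nothing says where its time or its birth is counted.

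If couples are sorted by the status they end up with, the outcome decides the group. A couple must go without success for long enough to be counted as having ceased, and a couple that conceives while waiting becomes one that never received NPT. Both effects arise without confounding and without any effect of NPT.

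Late consent adds a separate problem. A couple already treated at consent brings event-free time that it had to survive in order to be enrolled as still trying. Without delayed entry that time counts as time at risk. This affects the single-group curve as well as the comparison.

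**Working it through.** The plan gives no rates, power or event count for this comparison, so there is no figure to reproduce. The check asks what each reading gives when NPT does nothing.

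**Inputs.** From the documents: follow-up of 36 months (3b) and 45 women accrued (continuing review form). Assumed: 24-month live-birth conception rate 40%, mean wait to NPT 6 months, 20% never start, mean 18 months from start to stopping. Waits and stopping times are exponential and independent of fertility.

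**True values.** Monthly rate λ = −ln(1 − 0.40)/24 = 0.5108/24 = 0.0213. Every couple's true 12-month proportion is 1 − 0.6^0.5 = 22.5%, whatever its NPT status.

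**Ever versus never, by hand.**
- Would-be starters who conceive first: 0.8 × 0.0213/(0.0213 + 1/6) = 0.8 × 0.113 = 9.1% of all couples. Every one is a success, after a mean of 1/(0.0213 + 0.1667) = 5.3 months.
- True never-starters: 20%. The share with success by month 36 is 1 − 0.6^1.5 = 53.5%, so 10.7% of all couples. Their mean time at risk is 0.535/0.0213 = 25.1 months.
- Rate in the never group: (0.091 + 0.107)/(0.091 × 5.3 + 0.20 × 25.1) = 0.198/5.51 = 0.0359 per month.
- Couples who start keep the rate 0.0213 after starting. Ratio: 0.0213/0.0359 = 0.59.

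**Continuing versus ceased, by hand, with no end of follow-up.** The stopping rate is 1/18 = 0.0556 per month. Continuing couples all succeed, at rate 0.0213 + 0.0556 = 0.0768. Ceased couples carry 1/0.0768 = 13.0 event-free months on NPT and then 1/0.0213 = 47.0 months, giving 1/60.0 = 0.0167. The ratio is 4.6. Ending follow-up at 36 months brings it down to the simulated value below.

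**Simulation, 400,000 couples, grouped by eventual status.** NPT groups are timed from NPT start, and the never group from entry. Varying fertility means gamma variation between couples (CV 1) with the 24-month rate held at 40%.

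| Comparison | Rate ratio, constant fertility | Rate ratio, varying fertility | 24-month lifetable, constant fertility |
|---|---|---|---|
| Continuing vs ceased | 3.5 | 4.1 | 67% vs 26% |
| Ever vs never | 0.6 | 0.5 | 40% vs 58% |
| Continuing vs never | 1.3 | 1.2 | 67% vs 58% |

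Inputs were varied one at a time, with constant or varying fertility: 24-month rate 30–50%, mean wait 1–12 months, never start 10–40%, mean stopping time 9–36 months. The three ratios ran over 2.6–7.6, 0.36–0.86 and 0.79–2.6. The first two keep their direction; the third does not.

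**The other reading: current state, clock restarted at each change.** With constant fertility the 12-month proportions are all about 22.5%, so there is no bias. With varying fertility they are about 25%, 23% and 20% for not on, on and stopped, a modest bias.

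**Single-group curve under late consent.** Half the couples consent at the initial visit and half later (mean 3, 6 or 12 months), and NPT starts at the initial visit. Without delayed entry the 24-month 40% falls to about 34–38%. If NPT instead follows a mean 6-month wait, it falls to about 36–39%. Delayed entry at consent restores 40% in both cases.

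**One clock with time-dependent status.** The null hazard ratios are 0.99–1.01 in the base case and 0.95–1.04 over 216 combinations of inputs.

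**The case against.** The plan does not say that couples will be grouped by eventual status. Waiting and stopping in item 2b can be read as current states, and under that reading with constant fertility nothing is distorted. A reader might infer that 3.5 is the bias of the planned analysis. The documents do not support that: it is the cost of one reading that they leave open. The missing origin also bites mainly for couples never on NPT, since ceased couples do have a start date.

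A reader might also infer an inflated false-positive rate. The plan names no test for this comparison and disclaims hypothesis testing, so misleading description is the most that can be claimed.

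Nor do pregnancies still in progress at month 36 bias the plan as written. Its event is live birth, and in a birth-dated lifetable these are ordinary censoring at the end of follow-up (36-month estimate 43.9%, truth 43.9%). A problem arises only if events are re-dated to conception.

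The good null behaviour of the time-dependent model is partly built in, because the simulated switching is independent of fertility. With real couples, selection would remain.

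What stands is that three rules are missing from a comparison the plan places in its main outcome, and that the lifetable it names does not supply them.

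**Conclusion.** The concern holds in limited form and should be fixed. Item 3d lacks a time origin for couples never on NPT, a rule for changes of status, and delayed entry for late consent. The consequence depends on how the gap is filled. Grouping by eventual status gives large false differences; a clock restarted at each change of state gives none or a modest one.

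The direction for continuing versus ceased and for ever versus never follows from the grouping itself; every size rests on assumed rates. It would be wrong to treat the single-group NPT curve as safe: late consent pulls it down by about 2–6 percentage points at 24 months if half consent late and NPT starts at the initial visit. How many couples consented late is not given. Confidence is medium.

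**What to change.** 1. Do not compare couples by eventual status. Run one clock for every couple from the initial visit, with entry to the risk set at consent. Fit NPT status (not on, on, stopped) as a time-dependent covariate, and state in advance where other treatment belongs.
2. Apply delayed entry at consent to the single-group curve from NPT start as well.
3. For couples seeking to conceive, attribute a live birth to the status at conception. If the event is dated at conception, censor about 9 months before the end of ascertainment (month 27 of 36) or ascertain the later outcomes. A birth-dated lifetable needs no such rule. Report separately the couples who enter to maintain a pregnancy or who start NPT during one, because status at conception does not describe their exposure.
4. First confirm which dates were abstracted; item 16 lists only the titles of the forms. If stop or conception dates are missing, report only the single-group curve. If NPT start dates are missing too, report live birth from study entry for the whole cohort.

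**Cost.** SAP wording and some reprogramming; the continuing review form says analysis is still under way. With 45 women the base case expects about 8, 7 and 4–5 events while not on, on and stopped. The median 95% interval runs a factor of 3.6–3.9 either way for on versus stopped and 3.1 for on versus not on. Covariate adjustment will be very limited, and the comparison stays descriptive.

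### The main-outcome comparison of NPT with no or ceased NPT has only an unadjusted lifetable planned for it, although couples choose their own care

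*Combined protocol and SAP*

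**What the plan says.** Section 3d (Analysis of Main Outcome) defines the main outcome as the proportion with a live birth "at various time points up to five years after beginning treatment with NPT" and then sets out the comparison and its method: "compared to couples who do not receive NPT treatment, or who cease to receive NPT treatment. This will be analyzed by standard lifetable techniques". The purpose given for the method is censoring: "standard lifetable techniques to deal with censored data".

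The next sentence brings in regression for another purpose: "Cox proportional hazards regression will be used in an exploratory manner to investigate demographic and medical characteristics". It singles out woman's age, prior pregnancy and diagnoses as possible correlates of live birth. NPT status is not mentioned as a term. The section then repeats the same analyses for clinical pregnancy as a secondary outcome.

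On how couples reach their groups, section 2b says "Patients will receive whatever care they choose to receive", and section 2c states that there is no randomisation. Section 2b lists the comparators as couples who decline NPT, wait for it, receive other treatment or stop.

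Two statements lower the stakes. Section 2b says "This is an exploratory study rather than a hypothesis testing study", and the lay summary in section 2a says "We seek to document specific pregnancy rates for different factors such as age and type of infertility diagnosis".

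The continuing review form reports 45 women accrued (items 5 and 7), with follow-up finished and analysis and a manuscript in progress (item 13).

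**The concern.** A lifetable gives a valid curve for each group when censoring is uninformative. It does nothing about the groups being different kinds of couple. Here couples sort themselves: those who decline, wait, go elsewhere or stop may differ in age, history and diagnosis from those who start NPT and stay on it. The plan itself names these characteristics as likely correlates of live birth, but does not apply them to its own treatment contrast.

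The exploratory label means that no error rate is being spent. It does not remove confounding from a comparison that sits in the main outcome. If the curves are read as showing what NPT does, a difference in age mix would be read as a treatment effect.

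**Working it through.** **1. Is any adjustment planned?** The plan gives no power calculation, effect size or adjusted estimate for this contrast, so there is no figure to reproduce. The question is settled by reading.

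- Lifetable: assigned to the contrast; its stated purpose is censoring.
- Cox model: aimed at patient characteristics; NPT status not stated as a term.
- Rates by age and diagnosis (2a): show rates within strata; do not adjust the NPT contrast.
- Optional logistic model (3d, secondary outcomes): compares live birth with other pregnancy outcomes; not an NPT contrast.
- Matching, weighting, propensity scores or stratified comparison of NPT: none found.

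**2. How large could the bias be with no NPT effect?** All inputs here are assumed; none comes from the documents. Let older women have hazard *h* relative to younger women and make up a share *p1* of NPT couples and *p0* of comparators. The crude HR at the start of follow-up is

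HR = [(1 − p1) + p1·h] / [(1 − p0) + p0·h].

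- Mix (a), h = 0.5, p1 = 0.25, p0 = 0.50: (0.75 + 0.125) / (0.50 + 0.25) = 0.875 / 0.75 = 1.17. Reversed: 0.86.
- Mix (b), h = 0.4, p1 = 0.20, p0 = 0.60: (0.80 + 0.08) / (0.40 + 0.24) = 0.88 / 0.64 = 1.38. Reversed: 0.73.
- Age as a continuous variable, assumed HR 0.90 per year, gives similar sizes: a 1.5-year mean difference gives 0.90^−1.5 = 1.17, and 3 years gives 0.90^−3 = 1.37.

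For the gap in 3-year live birth, each group's proportion is 1 − [(1 − p)·exp(−L) + p·exp(−L·h)], with L solved so that the overall proportion is 30%, 40% or 50% and the NPT share is 50% to 80%.

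- Example, mix (a), 40% overall, share 50%: L = 0.644, giving 42.5% against 37.5%, a gap of 5.0 points.
- Across all settings: 3.9 to 5.7 points for (a) and 7.8 to 12.0 points for (b).

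These figures treat the groups as fixed. If couples also contribute off-NPT time by waiting or stopping, the crude HR shrinks. A simulation with no NPT effect (mean wait 6 months, 36 months of follow-up, with and without stopping and delayed entry, all assumed) gave 1.04 to 1.35.

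**3. How does this compare with the precision?** With 45 women and an assumed 30% to 50% live birth, events number 45 × 0.30 = 13.5 to 45 × 0.50 = 22.5. With *d* events and an NPT share *p*, the 95% CI for the HR runs from HR divided by a factor to HR multiplied by it, where the factor is exp[1.96 / √(d·p·(1 − p))].

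- d = 22.5, p = 0.5: exp(1.96 / √5.625) = 2.3.
- d = 13.5, p = 0.8: exp(1.96 / √2.16) = 3.8.

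The illustrated bias (a factor of 1.17 to 1.38) is smaller than this uncertainty.

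**4. Could one treatment state have very few events?** With no effect and event shares equal to group shares, an NPT share of 80% leaves 13.5 × 0.2 = 2.7 to 22.5 × 0.2 = 4.5 events off NPT. A 50% share leaves 6.75 to 11.25. Fewer than 5 is therefore a realistic case.

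**The case against.** The strongest reply has four parts.

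*The plan does not say the contrast will stay crude.* This is fair as to wording. A Cox model on the same outcome follows directly, and its covariate list is open. A reader might infer that adjustment is ruled out; the text does not support that. What stands is narrower: adjustment of the NPT contrast is not stated.

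*The study is exploratory and no NPT claim is announced.* This stands and lowers the severity. A reader might infer that the manuscript will claim an NPT effect. The continuing review form does not say what the manuscript covers, and the one finding it reports concerns appendix pathology.

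*The sizes rest on assumption.* They do. They show scale only, and the direction could be either way.

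*With 45 women, adjustment would change little that could be seen, and adjusting for age leaves prior pregnancy and diagnoses uncontrolled.* Both points are correct. They argue against expecting much from a model. They also argue against reading the crude curves as an NPT effect, so they support the labelling step.

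**Conclusion.** The concern holds at modest severity. The plan places a self-selected treatment comparison in its main outcome, and the only estimate it specifies for that comparison is unadjusted. Followed as written, this gives a comparison open to confounding, so the gap is more than a missing detail.

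Under the assumed age mixes, an HR of about 1.2 to 1.4, or its inverse, could appear with no NPT effect. That corresponds to roughly 4 to 12 points in 3-year live birth. The actual age mixes, and so the actual size and sign, are unknown.

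Two stronger conclusions are tempting and unsupported. One is that the results are biased in favour of NPT: nothing in the documents fixes the direction. The other is that an adjusted model would recover the true effect: it removes measured confounding by age only, and here it would be imprecise.

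The choice of time origin, late censoring of conceptions with unknown outcome, and the handling of women already pregnant at consent are separate questions. This point does not depend on them.

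**What to change.** 1. In section 3d, or in the analysis report if the plan is no longer amended, label the lifetable comparison by NPT status descriptive and unadjusted, and draw no statement about the effect of NPT from it. This costs one sentence.

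2. If a comparative estimate is reported, add NPT status and woman's age to the Cox model already planned.
   - Make NPT status time-varying, because waiting and stopping change during follow-up.
   - Use the conception analysis that section 3d already plans, so that status is read at conception and not after a pregnancy may have altered it. Say that the HR then refers to conception.
   - Keep couples on other treatment identifiable, and do not merge them silently with untreated couples.
   - Give the HR with its 95% CI, marked exploratory and post hoc, since follow-up is complete.

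3. If either treatment state has very few events, for example fewer than 5, report the contrast descriptively only.

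The costs of step 2 are data preparation with NPT start and stop dates, a wide interval (the crude factor is already 2.3 to 3.8), and residual confounding by prior pregnancy, diagnoses and reasons for stopping. Sections 2b and 3b say that interventions, conceptions and NPT records are followed. That they hold usable start and stop dates is an assumption to check first; if they do not, steps 1 and 3 still apply.
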